4.2 Exclusion criteria

Patients must not enter the study if any of the following exclusion criteria are fulfilled:

- 1. Intervention with any of the following:
 - Any investigational agents or study drugs from a previous clinical study within 30 days of the first dose of study treatment.

- Any cytotoxic chemotherapy from a previous treatment regimen within 21 days of the first dose of study treatment.
- Prior HDAC inhibitors (including romidepsin, belinostat and chidamide) or pralatrexate therapy within one week of the start of the study treatment.
- Corticosteroids at dosages equivalent to prednisone > 15 mg/day within 7 days of the start of the study treatment.
- Major surgery procedure (excluding placement of vascular access), or significant traumatic injury within 4 weeks of the first dose of study treatment, or have an anticipated need for major surgery during the study.
- Prior therapeutic anticancer antibodies (including brentuximab vedotin) within 4 weeks, other radio- or toxin-immunoconjugates within 10 weeks, radiation therapy within 3 weeks.
- Patient has undergone an allogeneic stem cell transplant. Patient had autologous stem cell transplant within 6 months.
- Prior treatment with a JAK or STAT3 inhibitor.
- Prior treatment with any onco-immunotherapy in 28 days prior to first dosing of AZD4205 (e.g. immune checkpoint inhibitors PD-1, PD-L1, CTLA-4). Other novel agents within clinical trials need to be evaluated by both investigator and Study Physician before enrollment).
- Live vaccines within 28 days prior to first dose.
- Patients currently receiving (or unable to stop use at least 1 week prior to receiving the first dose) vitamin K antagonists, anti-platelet agents or anticoagulated agents.
- Patients currently receiving (or unable to stop use at least 1 week prior to receiving the first dose) medications or herbal supplements known to be Potent inhibitors or inducers of CYP3A or sensitive substrates of BCRP or P-gp with narrow therapeutic index (see Appendix II).
- 2. Any unresolved toxicities from prior therapy, greater than Common Terminology Criteria for Adverse Events (CTCAE v 5.0) Grade 1 at the time of starting study treatment with the exception of alopecia.
- 3. Central nervous system or leptomeningeal lymphoma.
- 4. Patients with severely decreased lung function (i.e. any parameter of FEV1, and DLCO < 60% of predicted value). Past medical history of pneumonitis, drug-induced interstitial lung disease, radiation pneumonitis which required steroid treatment, or any evidence of clinically active interstitial lung disease.
- 5. Patients with disease condition which requires the treatment of immunosuppressants, biologics, or NSAIDs (non-steroid anti-inflammatory drugs).
- 6. Active infections including:

- History of known latent or active tuberculosis (TB), e.g. signs of active or latent TB on PPD test or chest X-ray/CT, skin test showing an induration of >10 mm or more, or positive results of screening tests according to local recommendations.
- Known infection with human immunodeficiency virus (HIV), or serologic status reflecting active hepatitis B or hepatitis C infection as follows:

	Inclusion	Exclusion
HIV antibody	Negative	Positive
HCV antibody	Negative	Positive
HBV	Both HBsAg and HBcAb are negative	Either HBsAg or HBcAb is positive

- Active viral infections (i.e. zoster) other than hepatitis B or C.
- Infections requiring oral or intravenous antimicrobial therapy or interferon.
- Bacterial infections including pneumonia within 30 days.
- 7. Any of the following cardiac criteria:
 - Congestive heart failure (CHF) per New York Heart Association (NYHA) classification > Class II (see Appendix I).
 - Clinically significant valvular diseases, hypertrophic or constrictive cardiomyopathy.
 - Any clinically significant abnormalities in rhythm, conduction or morphology of resting ECG, e.g., complete left bundle branch block, third degree heart block, and second-degree heart block, PR interval > 250 msec.
 - Cardiac ventricular arrhythmias requiring anti-arrhythmic therapy.
 - Acute Myocardial Infarction (AMI) within 6 months prior to starting treatment, unstable angina or new-onset angina.
 - Patients with heart transplant.
 - Mean resting corrected QTcF interval (QT_C) > 450 ms on screening triplicate electrocardiogram (ECG).
 - Patients with factors that increase the risk of QT prolongation or arrhythmic events (e.g., heart failure, hypokalaemia, congenital long QT syndrome, any concomitant medication known to prolong the QT interval (Appendix II)) or family history of long QT interval syndrome or unexplained sudden death under 40 years of age in first degree relatives).
 - Patients with previous/current thrombotic diseases such as pulmonary embolism, and deep venous thrombosis.
- 8. Another malignancy within 5 years prior to enrollment with the exception of adequately treated in-situ carcinoma of the cervix, uterus, basal or squamous cell carcinoma or non-melanomatous skin cancer.

- 9. Refractory nausea and vomiting if not controlled by supportive therapy, chronic gastrointestinal diseases, inability to swallow the formulated product or previous significant bowel resection that would preclude adequate absorption of AZD4205.
- 10. Women who are breast feeding.
- 11. History of hypersensitivity to active or inactive excipients of AZD4205 or drugs with a similar chemical structure or class
- 12. As judged by the investigator, any evidence of severe or uncontrolled systemic diseases, including uncontrolled hypertension or active bleeding diatheses. Screening for chronic conditions is not required.
- 13. Concurrent conditions that in the investigator's opinion would jeopardize compliance with the protocol.
- 14. Psychological, familial, sociological, or geographical conditions that do not permit compliance with the protocol.
- 15. Involvement in the planning and conduct of the study (applies to Sponsor staff or staff at the study site).

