4.3 Restrictions

4.3.1 Concomitant treatments

Information on any treatment within 4 weeks prior to starting of study treatment and all concomitant treatments given during the study along with reasons for the treatment will be recorded in the Case Report Form (CRF).

All patients must avoid concomitant use of medications, herbal supplements and/or ingestions of foods with known potent inducer/inhibitory effects on CYP3A activity whenever feasible. Such drugs must have been discontinued for an appropriate period before they enter screening and for a period after the last dose of AZD4205. Guidance on medications to avoid, medications that require close monitoring and on washout periods is given in Appendix II.

Patients taking concomitant medications whose disposition is dependent upon Breast Cancer Resistance Protein (BCRP) and which have a narrow therapeutic index should be closely monitored for signs of changed tolerability as a result of increased exposure of the concomitant medication whilst receiving study treatment. Patients may take cholesterol-lowering drugs if considered by the investigator to be medically indicated. Patients taking rosuvastatin should have creatinine phosphokinase levels monitored due to BCRP-mediated increase in exposure. If the patient experiences any potentially relevant AEs suggestive of muscle toxicity including unexplained muscle pain, tenderness or weakness, particularly if accompanied by malaise or fever, rosuvastatin must be stopped and any appropriate further management should be taken.

In vitro, AZD4205 demonstrated inhibition of kidney transporters including OCT2, MATE1 and MATE2-K, a clinically relevant drug-drug interaction (DDI) via inhibition of these transporters could not be discounted. Active secretion via kidney transporters are highly involved for metformin elimination, thus inhibition of these transporters has the

potential to interfere with the transport of metformin and ultimately affect both plasma and intracellular concentrations of metformin. Lactic acidosis, a rare but serious complication, can occur due to metformin accumulation (Please refer to Appendix II. GUIDANCE REGARDING POTENTIAL INTERACTIONS WITH CONCOMITANT MEDICATIONS for examples of drugs that are sensitive OCT2, MATE1 and MATE2-K substrates with narrow therapeutic index that fall into this category).

Patients must avoid live vaccines during the study.

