APPENDIX II. GUIDANCE REGARDING POTENTIAL INTERACTIONS WITH CONCOMITANT MEDICATIONS

The use of any natural/herbal products or other "folk remedies" (e.g. Ginseng and other Traditional Chinese Medicine) should be discouraged, but use of these products, as well as use of all vitamins, nutritional supplements, and all other concomitant medications must be recorded in the eCRF.

AZD4205 is an investigational drug for which no data on *in vivo* interactions are currently available in human. Based on *in vitro* data and predicted clinical exposure data, AZD4205 is considered unlikely to cause clinically significant drug interactions through inhibition or induction of cytochrome P450 enzyme activity.

In vitro data have shown that the principal CYP enzymes responsible for the Phase I metabolism of AZD4205 is CYP 3A4. Therefore, drugs strongly inhibiting CYP3A4/5 metabolism are recommended not to combine with AZD4205. Drugs inducing CYP3A4/5 metabolism should also be avoided to combine with AZD4205 if possible.

During the treatment of AZD4205, live vaccines should be avoided.

Drugs inhibiting CYP3A4/5 metabolism that Sponsor recommend are not combined with AZD4205.

The contribution of Phase I metabolism to the total clearance of AZD4205 is currently unknown but, to ensure patient safety, the following potent inhibitors of CYP3A4/5 must not be used during this study for any patient receiving AZD4205.

Table A1. Drug inhibiting CYP3A4/5

Contraindicated drugs	Withdrawal period prior to AZD4205 start
Ketoconazole, itraconazole, indinavir, saquinovir, nelfinavir, atazanavir, amprenavir, fosamprenavir, troleandomycin, telithromycin, fluconazole, nefazodone, cimetidine, aprepitant, miconazole, fluvoxamine	1 week
Amiodarone	27 weeks
Erythromycin, clarithromycin, verapamil, ritonavir, diltiazem	2 weeks

This list is not intended to be exhaustive, and a similar restriction will apply to other agents that are known to strongly modulate CYP3A4/5 activity. Appropriate medical judgment is required. Please contact Sponsor with any queries you have on this issue.

Patients should abstain from eating large amounts of grapefruit and Seville oranges (and other products containing these fruits, e.g., grapefruit juice or marmalade) during the study because of inhibition of intestinal CYP3A4 metabolism, e.g. no more than a small glass of grapefruit juice (120 mL) or half a grapefruit or 1 to 2 teaspoons (15 g) of Seville orange marmalade daily.

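### Exclusion 1 sets a 1-week minimum stop for potent CYP3A inhibitors, Appendix II Table A1 gives verapamil and diltiazem 2 weeks, and no text says which prevails

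*Protocol*

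**What the plan says.** Three places in the protocol bear on the stop.

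- **Section 4.2, exclusion 1.** It excludes "Patients currently receiving (or unable to stop use at least 1 week prior to receiving the first dose) medications or herbal supplements". The bullet is limited to agents "known to be Potent inhibitors or inducers of CYP3A", and it ends with a pointer to Appendix II.
- **Section 4.3.1.** Potent CYP3A inducers and inhibitors are to be avoided where feasible. Then: "Such drugs must have been discontinued for an appropriate period before they enter screening". No length is given; instead, "Guidance on medications to avoid, medications that require close monitoring and on washout periods is given in Appendix II".
- **Appendix II.** The lead-in to Table A1 reads: "to ensure patient safety, the following potent inhibitors of CYP3A4/5 must not be used during this study for any patient receiving AZD4205". The column for the stop is headed "Withdrawal period prior to AZD4205 start". Sixteen inhibitors have 1 week and amiodarone has 27 weeks. The row "Erythromycin, clarithromycin, verapamil, ritonavir, diltiazem" has 2 weeks. Table A2 gives inducers 3 weeks, or 5 weeks for phenobarbitone; its lead-in does not call them potent and asks only that they be avoided if possible.

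**The concern.** A site deciding eligibility works from the criteria, and Section 5.3.2 allows no exceptions to them. The number in the criterion is 1 week. The sponsor's own table, which gives patient safety as the reason for its restriction, has a longer period for some drugs of the same class. If the site applies the criterion's number, a patient can be enrolled and dosed inside the period that the sponsor set for withdrawal. Whether that patient is then a protocol deviation depends on which section is applied.

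What is at stake is eligibility and early safety. The protocol names CYP3A4 as the predominant P450 isoform for AZD4205 (Section 2.3.3) and reports QT increases in dogs at all doses tested (Section 2.3.2).

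**Working it through.** The plan gives no calculated figure to reproduce. The check is a comparison of texts, with day counts.

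**Inputs.** Minimum stop in exclusion 1: 7 days. Table A1 period for verapamil and diltiazem: 14 days. Cycle length: 21 days. Screening: up to 28 days before first dose (Section 3.1.3). Part B Day 1 ECGs: pre-dose and 1, 2, 4 and 8 hours after the dose (Section 6.4.3).

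**Step 1: same drugs, same clock.** Exclusion 1 is limited to potent inhibitors and inducers. The lead-in to Table A1 uses the same word for its inhibitors, so the table falls within the criterion. Both count back from the first dose. The periods can be compared directly.

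**Step 2: the gap.** 14 − 7 = 7 days. The sixteen 1-week inhibitors agree with exclusion 1.

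**Step 3: which drugs remain.** Six Table A1 entries exceed 1 week (5 + 1).

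- Amiodarone is caught elsewhere: Table A4 gives it 1 year, and exclusion 7 covers drugs known to prolong QT.
- Erythromycin and clarithromycin are in Table A4 too, but only at 2 days. What catches them is exclusion 6, which bars infections needing antimicrobials and bacterial infection within 30 days.
- Ritonavir is caught by the HIV criterion, assuming that is why it is taken.
- Verapamil and diltiazem are in neither Table A4 nor Table A5. Exclusion 7 bars ventricular arrhythmias that need anti-arrhythmic therapy and unstable or new-onset angina. Exclusion 12 bars uncontrolled hypertension. A patient taking either drug for controlled hypertension (an assumed use) passes all of these.

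That leaves 6 − 1 − 2 − 1 = 2 drugs.

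**Step 4: days inside the Table A1 period.** Let s be the number of days from stopping to Day 1. Exclusion 1 is met if s ≥ 7, and Table A1 if s ≥ 14. The two disagree for s = 7 to 13. Treatment days inside the period = 14 − s.

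| s | Days inside | Share of Cycle 1 |
|---|---|---|
| 7 | 7 (Days 1 to 7) | 7/21 = 33% |
| 8 | 6 | 6/21 = 29% |
| 13 | 1 (Day 1) | 1/21 = 5% |

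Every s from 7 to 13 puts Day 1, and so the serial ECGs, inside the period.

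**Step 5: room for a 14-day stop.** 28 − 14 = 14 days to spare within screening.

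**The case against.** The strongest reply is that the protocol already covers this. Exclusion 1 states a minimum and refers to Appendix II, and Section 4.3.1 adds a separate requirement that leads to the same table. A site that follows either pointer reaches the 2-week row, and by waiting 14 days before the first dose it satisfies both exclusion 1 and Table A1. This largely stands. A reader might infer that the protocol permits dosing after 7 days; it does not, because Section 4.3.1 still applies to a patient who passes exclusion 1. What the reply does not supply is a sentence making the longer period prevail. The pointer can equally be read as saying which drugs are covered, and Section 4.3.1 describes Appendix II as guidance.

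The reply also notes that the must-not-use sentence concerns use during treatment, not the length of washout, and that no harm is shown. Both are right. Appendix II itself says "The contribution of Phase I metabolism to the total clearance of AZD4205 is currently unknown". The introduction says that the spread across CYP3A and FMO may lessen such interactions. About 3-fold accumulation (Section 2.4) means that Day 1 exposure is well below steady state. Section 5.2.3 describes 250 mg as tolerated, although Section 3.2.2 reports a trend to more frequent and more serious adverse events than at 150 mg.

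Three stronger readings go beyond the documents.

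- **Inducers.** One might claim gaps of 21 − 7 = 14 days and, for phenobarbitone, 35 − 7 = 28 days. They arise only for an inducer regarded as potent, and the protocol does not mark which ones are.
- **Amiodarone.** The apparent gap of 189 − 7 = 182 days has no practical effect, because other provisions catch the drug.
- **Section 4.3.1.** One might read it as requiring 14 to 42 days for verapamil or diltiazem. That takes the Appendix II period, which is tied to first dose, and adds 0 to 28 days of screening. The section itself gives no number.

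**Conclusion.** The inconsistency is real, narrow and worth correcting. For verapamil and diltiazem the eligibility criterion is 7 days shorter than the sponsor's own withdrawal period, on the same clock and for drugs that the protocol itself calls potent. Up to 7 of 21 Cycle 1 days, always including the Day 1 ECGs, can fall inside that period.

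This rests on reading 1 week as the number a site may apply, and on there being patients who take either drug for a use that no other criterion bars. The number of such patients and the size of any exposure effect cannot be derived from the documents. They therefore do not support a conclusion that patients are harmed or that inhibition persists 7 to 13 days after stopping. ORR, power and alpha are unaffected.

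Separately, exclusion 1 and Appendix II count from first dose, while Section 4.3.1 counts from entry to screening. The sponsor should reconcile these, but the right direction is not obvious.

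**What to change.** In exclusion 1, for potent CYP3A inhibitors and inducers, replace the time limit with: *at least 1 week, or the longer withdrawal period in Appendix II where one is given, prior to receiving the first dose*.

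**Cost.** A patient on verapamil or diltiazem waits about one week longer than under the present criterion, within the existing screening window. For an inducer regarded as potent, the same clause would add 2 weeks, which also fits (28 − 21 = 7 days to spare). Phenobarbitone, if regarded as potent, would not fit (35 − 28 = 7 days over) and would have to be stopped before screening begins. Section 4.3.1 already has treatments in the 4 weeks before study treatment recorded, so a 14-day stop can also be checked for patients already dosed.

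**Section 4.3.1.** The sponsor should decide whether its washout counts from screening or from first dose. Moving it to first dose removes up to 28 days of waiting, which matters in an aggressive disease. It also relaxes the stricter rule and could let the screening ECG used for QTcF eligibility be taken while the patient is still on the interacting drug. That is a trade-off to settle, not a correction to make automatically.

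**Optional.** Mark in Table A2 which inducers count as potent for exclusion 1.

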4.3 Restrictions

4.3.1 Concomitant treatments

Information on any treatment within 4 weeks prior to starting of study treatment and all concomitant treatments given during the study along with reasons for the treatment will be recorded in the Case Report Form (CRF).

All patients must avoid concomitant use of medications, herbal supplements and/or ingestions of foods with known potent inducer/inhibitory effects on CYP3A activity whenever feasible. Such drugs must have been discontinued for an appropriate period before they enter screening and for a period after the last dose of AZD4205. Guidance on medications to avoid, medications that require close monitoring and on washout periods is given in Appendix II.

Patients taking concomitant medications whose disposition is dependent upon Breast Cancer Resistance Protein (BCRP) and which have a narrow therapeutic index should be closely monitored for signs of changed tolerability as a result of increased exposure of the concomitant medication whilst receiving study treatment. Patients may take cholesterol-lowering drugs if considered by the investigator to be medically indicated. Patients taking rosuvastatin should have creatinine phosphokinase levels monitored due to BCRP-mediated increase in exposure. If the patient experiences any potentially relevant AEs suggestive of muscle toxicity including unexplained muscle pain, tenderness or weakness, particularly if accompanied by malaise or fever, rosuvastatin must be stopped and any appropriate further management should be taken.

In vitro, AZD4205 demonstrated inhibition of kidney transporters including OCT2, MATE1 and MATE2-K, a clinically relevant drug-drug interaction (DDI) via inhibition of these transporters could not be discounted. Active secretion via kidney transporters are highly involved for metformin elimination, thus inhibition of these transporters has the

potential to interfere with the transport of metformin and ultimately affect both plasma and intracellular concentrations of metformin. Lactic acidosis, a rare but serious complication, can occur due to metformin accumulation (Please refer to Appendix II. GUIDANCE REGARDING POTENTIAL INTERACTIONS WITH CONCOMITANT MEDICATIONS for examples of drugs that are sensitive OCT2, MATE1 and MATE2-K substrates with narrow therapeutic index that fall into this category).

Patients must avoid live vaccines during the study.

Short-term corticosteroids at dosages equivalent to prednisone \leq 15 mg/day could be given to patients with B symptoms.

Given the mechanism of JAK inhibitors, the hepatic disorders are not considered as a significant risk for AZD4205, but cautions should be taken when acetaminophen or drugs containing acetaminophen are administered with AZD4205, and high dose/overdose of acetaminophen (propacetamol) or drugs containing acetaminophen (propacetamol) should be prohibited.

4.3.2 Supportive care and prophylactical therapy

Patients may receive any medication that is clinically indicated for treatment of adverse events, unless specifically excluded. All concomitant medications should be captured on the electronic CRF (eCRF).

- 1. Other anticancer agents, investigational agents and radiotherapy should not be given while the patient is receiving study treatment. The patient may be allowed to take localized palliative radiotherapy for pain control if it has been confirmed that there is no disease progression on the local lesion.
- 2. Blood transfusions are allowed at any time during the study treatment phase.
- 3. Granulocyte colony stimulating factors should not be used prophylactically during Cycle 1. Use of prophylactic colony stimulating factors may be considered after Cycle 1 following discussion with the Sponsor Study Physician.
- 4. Supportive care and other medications that are considered necessary for the patient's well-being, may be given at the discretion of the investigator.
- 5. Serious infection is an identified risk for the approved JAK inhibitors, and patients with relapsed or refractory PTCL are at a high risk of opportunistic infection. Pneumocystis pneumonia has been reported in the clinical study with AZD4205. Therefore, **for all patients during the treatment, pneumocystis prophylaxis is required**. Please follow institutional guidelines or European Conference on Infections in Leukemia (ECIL) guideline (Maertens J et al. 2016, Cordonnier C et al. 2016).
- 6. For patients with history of cytomegalovirus (CMV) infection that required treatment, prophylactic treatment and monitoring for reactivation via serology or viral load detection per institutional guidelines is recommended.
- 7. For patients with tumor response during the study, it is not recommended to subsequently receive bone marrow transplantation, e.g. autologous or allogenic stem cell transplantation (SCT). If patients require SCT, AZD4205 should be discontinued

after discussion with sponsor study physician, and tumor response assessment should still be performed as scheduled after discontinuation.

